5.7.2 Pharmacokinetics of CBD and its Major Metabolites

Samples for PK analysis are taken on Visit 3 (first dose, Day 1) and Visit 10 (last maintenance dose of the blinded phase, Day 113) for patients weighing more than 20 kg. For patients recruited under Protocol Version 2, PK samples were taken at the following time-points:

- Prior to administration of IMP, ≤ 0.0 hours pre-dose on Visit 3 or C_{trough} at steady state (Visit 10).
- ≥ 4.0 hours to ≤ 5.0 hours.
- ≥ 6.0 hours to ≤ 7.0 hours.
- ≥ 8.0 hours to ≤ 10.0 hours, for patients 18 years or older.

Patients recruited under Protocol Version 3 onwards, PK samples were taken at the following time-points:

- Prior to administration of IMP, ≤ 0.0 hours pre-dose on Visit 3 or C_{trough} at steady state (Visit 10).
- ≥ 2.0 hours to ≤ 3.0 hours.
- ≥ 4.0 hours to ≤ 6.0 hours.
- ≥ 8.0 hours to ≤ 10.0 hours, for patients 18 years or older.

The nominal mid-point time of 0, 2.5, 4.5, 5, 6.5 and 9 hours will be used for summaries of plasma concentrations. Plasma concentrations and PK parameters will be summarized showing the number of non-missing values (n), arithmetic mean, standard deviation, coefficient of variation (%), median, minimum and maximum. Where samples are reported as BLQ, a value of zero will be used in the summaries. Summary statistics will be presented to 3 significant figures.

Where data allow, the PK parameter AUC_{0-t} will be derived at each visit by the PK vendor. A dose-normalized AUC_{0-t} will be calculated as AUC_{0-t} divided by the randomized dose per administration (12.5 or 25 mg/kg). This will include Visit 3, for consistency, where the first dose of IMP will be 2.5 mg/kg.

Plasma concentrations of CBD and its major metabolites 7-hydroxy-CBD (7-OH-CBD) and 7-carboxy-CBD (7-COOH-CBD) will be summarized by nominal mid-point time, visit and GWP42003-P arm. In addition, a dot plot of plasma concentrations for each patient, by nominal mid-point time will be created for each visit and GWP42003-P arm. The arithmetic mean will be highlighted on the plot. Additionally, a line plot of the arithmetic mean plasma concentration will be created with standard error bars by nominal mid-point time for each visit and GWP42003-P arm. These plots will be presented both a linear and semi-logarithmic scale for plasma concentration.

AUC_{0-t} and dose normalized AUC_{0-t} , for CBD and its major metabolites 7-OH-CBD and 7-COOH-CBD, will be summarized by visit and GWP42003-P arm. In addition, the ratio of 7-OH-CBD AUC_{0-t} to CBD AUC_{0-t} and the ratio of 7-COOH-CBD AUC_{0-t} to CBD AUC_{0-t} will be summarized. Box plots of AUC_{0-t} will be produced comparing visit on the x-axis, by parent and metabolite, and GWP42003-P arm. This will be repeated with parent and metabolite on the x-axis, by visit and GWP42003-P arm. Summaries and plots of AUC_{0-t} will be repeated by stratified age group.

Plasma concentration and AUC_{0-t} summaries may exclude individual time-points or visits for patients deemed to meet certain criteria that could affect exposure. These criteria include:

- Patients vomiting on or 1 day prior to the PK visit.
- Missed doses prior to the PK visit.
- IMP dose reduction.
- Cases of severe diarrhoea.
- Use of disallowed concomitant medication.

All exclusion will be detailed in a separate document finalized prior to unblinding. All data will be listed with data excluded from summaries flagged along with the reason for exclusion.

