## 8.1.2 Dose Escalation and Dose Adjustments

All patients will be weighed during Visit 3 and the daily volumes of IMP solution to be taken during the maximum four-week titration period and for the remainder of the blinded phase maintenance period will be calculated via the IVRS and the dosing regimen provided to the patient and/or caregiver. Doses may be altered during the OLE according to changes in patient weight. Further information on dispensing procedures will be provided in a separate Pharmacy Manual.

Titration from 0–25 mg/kg/day will begin at 5 mg/kg/day and will be increased in increments of 5 mg/kg/day every two days (patients will remain on each dose level for two days before they progress on to the next dose). Titration from 25–50 mg/kg/day will continue at smaller increments of 2.5 mg/kg/day every two days.

Table 8.1.2-1Dose Titration Regimen*			
Day	Dose Level 1 (25 mg/kg/day)	Dose Level 2 (50 mg/kg/day)	
1	5.0 mg/kg	5.0 mg/kg	
2	5.0 mg/kg	5.0 mg/kg	
3	10.0 mg/kg	10.0 mg/kg	
4	10.0 mg/kg	10.0 mg/kg	
5	15.0 mg/kg	15.0 mg/kg	
6	15.0 mg/kg	15.0 mg/kg	
7	20.0 mg/kg	20.0 mg/kg	
8	20.0 mg/kg	20.0 mg/kg	
9	25.0 mg/kg	25.0 mg/kg	
10	25.0 mg/kg	25.0 mg/kg	
11	25.0 mg/kg	27.5 mg/kg	
12	25.0 mg/kg	27.5 mg/kg	
13	25.0 mg/kg	30.0 mg/kg	
14	25.0 mg/kg	30.0 mg/kg	
15	25.0 mg/kg	32.5 mg/kg	
16	25.0 mg/kg	32.5 mg/kg	
17	25.0 mg/kg	35.0 mg/kg	
18	25.0 mg/kg	35.0 mg/kg	
19	25.0 mg/kg	37.5 mg/kg	
20	25.0 mg/kg	37.5 mg/kg	
21	25.0 mg/kg	40.0 mg/kg	
22	25.0 mg/kg	40.0 mg/kg	
23	25.0 mg/kg	42.5 mg/kg	
24	25.0 mg/kg	42.5 mg/kg	
25	25.0 mg/kg	45.0 mg/kg	
26	25.0 mg/kg	45.0 mg/kg	
27	25.0 mg/kg	47.5 mg/kg	
28	25.0 mg/kg	47.5 mg/kg	
29	25.0 mg/kg	50.0 mg/kg	

IMP is to be taken twice daily. Total daily doses are shown.

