#### 9.2.9.1 Pharmacokinetic Blood Sampling

The plasma concentration/time curves of CBD and its major metabolites will be assessed at Visits 3 and 10 for patients weighing more than 20 kg. Where appropriate, blood samples will be taken as follows:

- One sample pre-dose (i.e., prior to administration of IMP).
- One sample between 2 and 3 hours post-dose.
- One sample between 4 and 6 hours post-dose.
- One sample between 8 and 10 hours post-dose (patients 18 years and above only).

There must be a minimum period of at least two hours between each of the blood sampling time points. In the event of an AE that, in the opinion of the investigator, is related to a concomitant AED, additional blood samples may be collected.

For patients who undergo PK blood sampling, the patient/caregiver will record all meal times and the types of meals consumed by the patient during all PK testing days (Visits 3 and 10).

Analysis of all pharmacokinetic samples will be conducted at a central clinical laboratory. Sample volume requirements and processing procedures will also be detailed in a separate laboratory manual. The patient/caregiver must be advised that it may not be safe for them to undertake further blood tests within one month of any study-related blood draws and to inform the investigator if they suffered any blood loss during the one-month period leading up to a planned blood draw.

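### Visit 3 dose-normalized AUC is divided by the randomized target dose, not the 2.5 mg/kg given, so it is 5-fold or 10-fold too low and shows a false 2-fold arm difference

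*SAP*

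**What the plan says.** SAP section 5.7.2 has AUC0-t derived at two visits: "Samples for PK analysis are taken on Visit 3 (first dose, Day 1) and Visit 10", the latter on Day 113 at the last maintenance dose of the blinded phase. The dose-normalized version is AUC0-t "divided by the randomized dose per administration (12.5 or 25 mg/kg"). The next sentence extends this to Day 1: "This will include Visit 3, for consistency, where the first dose of IMP will be 2.5 mg/kg".

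The results for CBD and its two major metabolites "will be summarized by visit and GWP42003-P arm". The SAP's list of tables gives the PK parameter summary (Table 14.8.2.1) both overall and by age group.

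Protocol section 8.1.2 gives the Day 1 dose: "Titration from 0–25 mg/kg/day will begin at 5 mg/kg/day". Table 8.1.2-1 shows 5.0 mg/kg on Day 1 at both dose levels, with the note "IMP is to be taken twice daily. Total daily doses are shown".

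**The concern.** Dose normalization divides an exposure by the dose that produced it, so that exposures after different doses can be compared. Here the SAP names the dose given at Visit 3 and then divides by a different one, which the patient does not reach until titration is complete.

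The protocol's exploratory PK objective covers both single and multiple doses, and Visit 3 is the single-dose half. A reader who sees normalized AUC tabulated by visit and arm would naturally use it to judge accumulation (Visit 10 against Visit 3) and dose proportionality (one arm against the other). At Visit 3 both the level and the arm contrast would be wrong.

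**Working it through.** **Inputs**

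- Day 1 dose, both dose levels: 5 mg/kg/day in two administrations (Protocol section 8.1.2 and Table 8.1.2-1).
- Target doses: 25 and 50 mg/kg/day, also twice daily.
- SAP divisors: 12.5 and 25 mg/kg (section 5.7.2).
- PK sampling at Visit 3 follows the first administration. The latest post-dose sample is "One sample between 8 and 10 hours post-dose (patients 18 years and above only"), per Protocol section 9.2.9.1. The relevant dose is therefore the single administration.

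**Reproducing the plan's own figures**

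Dose per administration = daily dose / 2:

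- Day 1: 5/2 = 2.5 mg/kg
- 25 mg/kg/day arm: 25/2 = 12.5 mg/kg
- 50 mg/kg/day arm: 50/2 = 25 mg/kg

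The volume rule in SAP section 5.6.1 agrees. Weight/8 and weight/4 mL per administration, at the 100 mg/mL in Protocol section 5.1, give 100/8 = 12.5 and 100/4 = 25 mg/kg. The three dose figures are correct; the fault lies in which one is used as divisor at Visit 3.

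**Error in level at Visit 3**

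Understatement = SAP divisor / dose given:

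- 25 mg/kg/day arm: 12.5/2.5 = 5
- 50 mg/kg/day arm: 25/2.5 = 10

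Daily totals give the same factors: 25/5 = 5 and 50/5 = 10.

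**Error in the arm contrast at Visit 3**

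Suppose both arms have a raw AUC0-t of 100 (illustrative units) after the same 2.5 mg/kg dose:

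| Arm | SAP divisor | Dose given as divisor |
|---|---|---|
| 25 mg/kg/day | 100/12.5 = 8 | 100/2.5 = 40 |
| 50 mg/kg/day | 100/25 = 4 | 100/2.5 = 40 |
| Ratio, 25 to 50 | 8/4 = 2.0 | 40/40 = 1.0 |

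The lower-dose arm appears to have twice the normalized exposure on a day when the arms take the same dose.

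**Error in Visit 10 against Visit 3**

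Within an arm the SAP uses one divisor at both visits, so it cancels and the ratio of normalized values equals the ratio of raw values. The 5-fold or 10-fold rise in dose is left unadjusted. If exposure were proportional to dose with no accumulation (an illustrative assumption), the ratio should be 1:

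- 25 mg/kg/day arm: (12.5/12.5) / (2.5/12.5) = 5
- 50 mg/kg/day arm: (25/25) / (2.5/25) = 10

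**The case against.** The best defence is that this is a disclosed convention and not a slip. The SAP states the divisor, then the true Visit 3 dose, and gives a reason. Because the divisor is constant within an arm, a reader can recover the correct Visit 3 value by multiplying by 5 or 10.

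The protocol's PK endpoints ask for concentrations and AUC0-t, not a normalized AUC. The SAP plans no accumulation index, no dose-proportionality analysis and no test. Raw AUC0-t is summarized by visit and arm beside the normalized version. Concentration summaries, AUC box plots and metabolite-to-parent ratios are untouched. By age group, only the normalized rows of Table 14.8.2.1 are affected. PK is exploratory and limited to patients over 20 kg.

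All of that stands, and it limits the importance. It does not rescue the definition: disclosure does not make the Visit 3 figure dose-normalized, and consistency across visits means dividing by the dose given at each one. If division by 2.5 mg/kg was intended, the text needs correcting anyway, since a programmer would follow the stated divisors.

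Visit 10 deserves separate treatment. For patients on target dose the divisor is right. Dose reduction is a listed reason for leaving a visit out of the summaries, with exclusions fixed before unblinding. The wording only permits exclusion, however, and any dose-reduced patient who is kept would be divided by a dose not taken. Whether there are any cannot be known from the documents.

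**Conclusion.** The definition is wrong as written. Visit 3 dose-normalized AUC0-t is 5-fold too low in the 25 mg/kg/day arm and 10-fold too low in the 50 mg/kg/day arm, for CBD and both metabolites. Equal exposure after the same dose is reported as a 2-fold arm difference. These factors rest only on the SAP's divisors and the common Day 1 dose, so they hold for every patient who takes the scheduled first dose. The Visit 10 to Visit 3 ratios of 5 and 10 where 1 would be right also need the illustrative assumption of dose-proportional exposure without accumulation.

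The Visit 10 problem is conditional on dose-reduced patients remaining in the summaries. The correction should be made, but no primary, key secondary or safety conclusion depends on it.

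**What to change.** In SAP section 5.7.2, define dose-normalized AUC0-t as AUC0-t divided by the dose in mg/kg actually taken at the administration that precedes sampling: 2.5 mg/kg at Visit 3 in both active arms, and the recorded dose at Visit 10. Delete the sentence that carries the randomized divisor over to Visit 3. Omitting the normalized value at Visit 3 would also remove the error, but would lose the single-dose comparison.

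For Visit 10, add a line on the derivation. The diary records the volume taken each day (Protocol section 8.4) and the volumes are set from Visit 3 weight (Protocol section 8.1.2). The SAP should therefore say how the daily volume becomes a dose per administration and which weight converts it to mg/kg.

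The cost is one changed divisor for Visit 3 and a short derivation for Visit 10, with no new data collection. No dosing or clinical rule changes.

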#### **PK (Double-blind only):**

- The plasma concentrations will be summarized by time window for CBD and its major metabolites following single and multiple doses of GWP42003-P.
   Where data allows, the area under the plasma concentration curve (AUC0-t) from time zero to the last measurable time-point will be calculated.
- Plasma concentrations of concomitant AEDs before and after treatment with GWP42003-P, where available.

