Table 13.3.2	Shift Table for Biochemistry Laboratory Parameters – Based on Toxicity Limits	Safety Analysis Set
Table 13.3.3	Shift Table for eGFR – Based on Derived Grades	Safety Analysis Set
Table 13.4	Summary of Liver Parameter Flags	Safety Analysis Set
Table 13.5	Incidence of Laboratory Abnormalities	Safety Analysis Set
Table 13.6	Summary of Pregnancy Test and Urine THC Screen Results	Safety Analysis Set
Table 14.1.1	Summary of Vital Signs	Safety Analysis Set
Table 14.1.2	Incidence of Clinically Significant Changes from Baseline for Vital Signs	Safety Analysis Set
Table 14.1.3	Incidence of Defined Flagged Vital Signs	Safety Analysis Set
Table 14.1.4	Incidence of Vital Signs Abnormalities	Safety Analysis Set

Table Number	Title	Analysis Set
Table 14.2.1	Summary of ECG Parameters	Safety Analysis Set
Table 14.2.2	Incidence of Defined Flagged ECG Parameter Values	Safety Analysis Set
Table 14.2.3	Incidence of ECG Abnormalities	Safety Analysis Set
Table 14.3	Summary of Columbia-Suicide Severity Rating Scale by Type	Safety Analysis Set
Table 14.4	Incidence of Physical Examination Abnormalities	Safety Analysis Set
Table 14.5	Summary of Tanner Stages	Safety Analysis Set
Table 14.6	Summary of Menstruation Details	Safety Analysis Set
Table 14.7	Summary of Patients with Inpatient Hospitalizations due to Epilepsy	Safety Analysis Set
Table 14.8.1	Summary of Plasma Concentrations	Safety Analysis Set
Table 14.8.2.1	Summary of PK Parameters (Overall and by Age Group)	Safety Analysis Set
Table 14.8.2.2	Summary of PK Parameter Metabolite to Parent Ratio (Overall and by Age Group)	Safety Analysis Set
Table 14.9	Summary of Plasma Concentrations of Concomitant Antiepileptic Drugs	Safety Analysis Set
Table 14.10	Summary of Study Medication Use and Behavior Survey	Safety Analysis Set
Table 14.11.1	Summary of Supplemental Drug Accountability Form	Safety Analysis Set
Table 14.11.2	Summary of Supplemental Adverse Event Form	Safety Analysis Set
Table 14.11.3	Summary of Site Classification Form	Safety Analysis Set

Table 18 List of OLE Phase Tables

Table Number	Title	Analysis Set
OLE Table 1.1.1	Summary of Patient Disposition by Site	OLE Safety Analysis Set
OLE Table 1.1.2	Summary of Patient Disposition During by Country	OLE Safety Analysis Set
OLE Table 1.2	Summary of Overall Patient Disposition	OLE Safety Analysis Set
OLE Table 2	Summary of Important Protocol Deviations	OLE Safety Analysis Set
OLE Table 3.1	Summary of Demographic Data	OLE Safety Analysis Set

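### AUC0-t ends later in adults than in patients under 18, so the SAP's pooled and by-age AUC summaries confound age with sampling duration (about 1.4 to 2.2-fold from Protocol Version 3 onwards and 1.2 to 1.6-fold under Version 2, on assumed profiles)

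*SAP*

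**What the plan says.** The PK endpoint (Protocol 4.1.2, repeated in SAP 3.3.3) is the area "from time zero to the last measurable time-point will be calculated", where data allow. Its upper limit is therefore set by each patient's own sampling.

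The sampling differs by age. In Protocol 9.2.9.1 the last sample open to every age is "One sample between 4 and 6 hours post-dose"; the 8-10 h sample is taken only from age 18. SAP 5.7.2 gives two schemes:

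- **Protocol Version 3 onwards:** the last sample under 18 is "≥ 4.0 hours to ≤ 6.0 hours".
- **Protocol Version 2:** the last sample under 18 is "≥ 6.0 hours to ≤ 7.0 hours".
- **Both:** a final sample at "≥ 8.0 hours to ≤ 10.0 hours, for patients 18 years or older".

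SAP 5.7.2 then summarises AUC0-t and dose-normalized AUC0-t by visit and active arm with all ages together, and states that summaries and plots of AUC0-t "will be repeated by stratified age group". In SAP Appendix 6, Table 14.8.2.1 (PK parameters) and Table 14.8.2.2 (metabolite-to-parent ratios) are each planned overall and per age group, with one box plot per stratum. The strata are 1-6, 7-11, 12-17 and 18-65 years. No common end time, partial AUC or dosing-interval AUC is planned. The listed PK exclusions (vomiting, missed doses, dose reduction, severe diarrhoea, disallowed medication) do not concern sampling duration.

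**The concern.** The age at which the late sample begins is also the lower limit of the oldest stratum. Every adult AUC therefore covers a longer interval, by design, than every AUC from a patient under 18 in the same scheme: about 4 hours longer from Version 3 onwards (9 - 5) and 2.5 hours under Version 2 (9 - 6.5). Equal exposure would look higher in adults, and truly lower adult exposure could look equal. The pooled summary mixes durations, so its level depends on the mix of ages and protocol versions.

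Dose normalization does not help: within an arm it divides every patient's AUC by the same randomized dose. Metabolite-to-parent ratios may shift too, because parent and metabolite curves need not have the same shape. Concentrations by nominal time (Table 14.8.1) are not split by age, so the AUC-based outputs are the only planned PK summaries by age, in a mg/kg-dosed trial that enrols from age 1 to 65.

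**Working it through.** **Step 1: the plan's own figures.** Mid-points of the SAP windows are (2+3)/2 = 2.5, (4+6)/2 = 5 and (8+10)/2 = 9 h from Version 3 onwards, and (4+5)/2 = 4.5, (6+7)/2 = 6.5 and 9 h for Version 2. With 0 h these are exactly the nominal times in SAP 5.7.2. The documents give no Tmax, half-life or concentrations, so every profile below is an assumption. Pharmacokinetics are taken as identical at all ages, and all planned samples as taken and measurable.

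**Step 2: flat profile.** AUC = C x t, so the adult/under-18 ratio is the ratio of end times.

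- Version 3 onwards: 9/5 = 1.80. At the window limits, 8/6 = 1.33 to 10/4 = 2.50.
- Version 2: 9/6.5 = 1.38. At the window limits, 8/7 = 1.14 to 10/6 = 1.67.

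**Step 3: three worked profiles**, linear trapezoid at nominal times. Concentrations relative to peak are given at 0, 2.5, 5 and 9 h. For Version 2 the same curves are read off linearly at 4.5 and 6.5 h.

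| Assumed profile | V3+ AUC0-5 | V3+ AUC0-9 | Ratio | V2 AUC0-6.5 | V2 AUC0-9 | Ratio |
|---|---|---|---|---|---|---|
| Visit 3, slow decline: 0, 1, 0.8, 0.5 | 3.500 | 6.100 | 1.74 | 3.418 | 4.902 | 1.43 |
| Visit 3, fast decline: 0, 1, 0.5, 0.2 | 3.125 | 4.525 | 1.45 | 2.338 | 3.072 | 1.31 |
| Visit 10, with trough: 0.5, 1, 0.8, 0.6 | 4.125 | 6.925 | 1.68 | 4.580 | 6.236 | 1.36 |

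First row, Version 3 onwards: 0.5 x 2.5 x (0+1) + 0.5 x 2.5 x (1+0.8) = 3.5; adding 0.5 x 4 x (0.8+0.5) = 2.6 gives 6.1.

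**Step 4: a grid.** One-compartment oral model, Tmax 1.5-6 h, half-life 2-60 h, trapezoid at nominal times, 12-hourly dosing assumed for steady state.

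| Scheme | Single dose (Visit 3) | Steady state (Visit 10) |
|---|---|---|
| Version 3 onwards | 1.39-2.22, median 1.96 | 1.38-1.81, median 1.76 |
| Version 2 | 1.24-1.59, median 1.52 | 1.23-1.39, median 1.37 |

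Near-exact integration over a smaller grid gives 1.36-2.03 and 1.35-1.78 from Version 3 onwards, and 1.16-1.45 and 1.16-1.37 for Version 2, so the effect does not come from the sparse trapezoid. Hand-drawn shapes outside the grid go further: (0, 1, 0.4, 0.1) gives 4/3 = 1.33 and (0, 0.3, 1, 1) gives 6/2 = 3.0.

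**Step 5: pooled mean.** With adult share p and ratio r, the mean relative to a common end time is 1 + p(r - 1). For r = 1.8 and p of 20-40% (assumed): 1 + 0.2 x 0.8 = 1.16 to 1 + 0.4 x 0.8 = 1.32.

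**Step 6: can Version 2 be brought to 5 h?** Version 2 has no 2-3 h sample, so its trapezoid runs straight from 0 to 4.5 h. Interpolated to 5 h, the three profiles give 2.30/3.5 = 0.66, 1.64/3.125 = 0.52 and 3.43/4.125 = 0.83 of the Version 3 value, although the underlying curve is the same.

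**Step 7: common end time within a scheme.** Adults and younger patients then contribute the same nominal times, and the ratio with identical pharmacokinetics is 1.0.

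**The case against.** The strongest reply is that this is an exploratory, descriptive PK presentation. The PK objective is single- and multiple-dose pharmacokinetics, with no stated child-adult exposure question. No test or ratio between age groups is planned, and each stratum has its own figure, with visit or analyte on the x-axis. Individual concentrations and parameters are listed (Listings 14.9.1 and 14.9.2), so anyone could derive a common-time AUC later, and a footnote giving end times might prevent misreading. All of that stands as a limit on importance. It does not make the planned summaries comparable: the table titles do not say that the end time differs, and a footnote would warn without supplying a usable figure.

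Four stronger readings are tempting and are not supported:

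- **That all patients under 18 stop at 4-6 h.** Version 2 patients have a 6-7 h sample.
- **That a fixed adult excess of, say, 1.5 to 2.2 follows from the design alone.** The design fixes the durations; the ratio needs a profile, and the documents give none. The top of the range needs a single dose with a late peak.
- **That Version 2 AUCs under 18 run 6.5/5 = 1.3 times those from Version 3 onwards.** This needs a flat curve, which is impossible after a first dose from zero. The Step 3 Visit 3 profiles give 3.418/3.5 = 0.98 and 2.338/3.125 = 0.75; the Visit 10 profile gives 4.58/4.125 = 1.11.
- **That arm comparisons or efficacy results are affected.** Randomization is stratified by age, so the age mix should be similar across arms.

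**Conclusion.** The concern holds for the overall and by-age summaries and plots of AUC0-t, and for the outputs derived from them. Adult versus younger is fully confounded with AUC duration. With identical pharmacokinetics at nominal times, the expected adult/under-18 ratio is about 1.4-2.2 from Version 3 onwards (1.8 if flat, at most about 1.8 at steady state) and about 1.2-1.6 under Version 2 (1.38 if flat). Equally, with a flat profile from Version 3 onwards, adult exposure at 1/1.8 = 0.56 of that in younger patients would look the same as theirs.

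These sizes depend on the assumed Tmax and half-life range and on samples near mid-window. If single patients at opposite window limits are compared, the Version 2 ratio can fall slightly below 1 (0.94). The number of patients recruited under Version 2 and the adult share of the PK set are not given.

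Comparisons between arms, between visits within a patient, and among the under-18 strata within one protocol version are largely unaffected. The primary analysis is untouched. The change is worth making because it needs only existing samples.

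**What to change.** In SAP 5.7.2, and in the matching tables and box plots of Appendix 6, base the overall and age-group presentations of AUC, dose-normalized AUC and metabolite-to-parent ratios on a partial AUC to one end time reached by all ages within each sampling scheme:

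- **Version 3 onwards:** nominal 0-5 h, or 0-4 h on actual times, since the last under-18 sample may be as early as 4.0 h.
- **Version 2:** nominal 0-6.5 h, or 0-6 h on actual times, for the same reason at 6.0 h.

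Show the two schemes separately. Do not interpolate Version 2 to 5 h: Step 6 shows that this replaces an age artefact with a protocol-version artefact. Report AUC0-t to 8-10 h only in a table labelled as patients aged 18 and over.

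The cost is one more derived parameter from samples already planned, the adults' last sample left out of the common-time AUC (it stays in the adult table), and smaller groups once split by scheme.
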